Study visits will occur at screening (Visit 1), beginning of the second study phase (day 14-21, Visit 2) and study conclusion (day 35-40, Visit 3). Each of these visits will include medical history review by study personnel, a physical exam performed by a licensed study physician, and the collection of vital signs. Visit 1 will include a dietetic assessment to be completed with a Celiac Center dietician. This dietetic assessment will occur either in-person at Visit 1 following the consent or following Visit 1 over the phone prior to the start of the study medication. The purpose of this dietetic assessment is to (1) evaluate for recent gluten exposure and obvious other food intolerances (e.g. moderate lactose intolerance, FODMAP intolerance), and (2) educate the subject regarding the diet they should follow while on the study.

At Visit 1 participants will be asked to complete the CeD-GSRS, CSI, and CDAT questionnaires. Following Visit 1, participants will be asked to complete the CSI once each day for the duration of the study period. Participants will additionally complete the CeD-GSRS and a specialized CSI that includes a question regarding potential gluten exposure at the end of each study phase, i.e at days 7, 17, 24, and 34 (please see the protocol schema on page 14 below for a depiction of the study phases).

If participants do not attend Visit 2 until after study day 17 they will be instructed to stop taking study medication, including omeprazole if prescribed for the study, until they attend Visit 2 and can receive the placebo washout.

Participants will additionally complete a daily medication log to record when they take the study medication and a daily paper stool log to record bowel movement frequency and consistency.

Participants will be contacted every 3 (±1) days after enrollment for safety and compliance assessments (e.g. medication, symptoms survey, and stool log review).

Laboratory Assessments:

Safety outcomes will be assessed at visit 1 (screening) and 3 (study conclusion) and will include:

- Celiac serologies (IgA tTG and IgA/IgG DGP)
- Complete blood count (CBC)
- Basic metabolic panel (BMP)

Fecal elastase will additionally be assessed at Visit 1. Stool sampling for fecal elastase testing will occur at Visit 1 when possible or a stool sample will be returned at Visit 2.

Female subjects will be asked to provide a urine sample at Visit 1 for β-HcG pregnancy testing.

Safety Evaluations:

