Supplemental information shall be submitted as soon as available and may include laboratory results, radiology reports, progress notes, hospital admission and emergency room notes, holding and observation notes, discharge summaries, autopsy reports, and death certificates.

Regarding the reporting of pregnancy: Study center personnel will report every pregnancy on a pregnancy report form as soon as possible (within 24 hours of first awareness of the pregnancy to the pregnancy fax number, [name]), even if no AE has occurred, and follow it to term. If, however, the pregnancy is associated with an SAE (e.g. if the mother is hospitalized for dehydration), in addition to the pregnancy report form, a separate SAE report form will be filed.

All relevant SAE or pregnancy information will be faxed to the Forest Global Drug Safety Department at **[contact]**.

B. Statistical Considerations

Sample Size Justification:

As this is a pilot study and the response of celiac symptoms to pancreatic enzyme supplementation has never been assessed, sample size is not possible to definitively calculate. However, based on the literature, a standard deviation of σ =0·55 is estimated and a >0.4 point change in CeD-GSRS can be considered clinically significant. Allowing for a type-1 error rate of α =0·05, and assuming a 10% drop-out rate, 32 total participants would provide 80% power to detect a 0·4-point difference in CeD-GSRS score between pancreatic enzyme treatment and placebo using a two treatment cross over design. Allowing for drop out and treatment non-compliance we plan to recruit until 30 participants have completed the treatment phases, up to a maximum of 40 eligible individuals. While this may appear somewhat overpowered, this sample size is feasible and allows for what is a very high degree of uncertainty regarding both the possible treatment effect and the influence of fecal elastase levels on efficacy, as described below.

Data Analysis:

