Efficacy analyses will include all patients receiving ≥1 dose of study drug during double-blind treatment and with ≥1 post-baseline assessment (Modified Intent-to-Treat [MITT] population). Baseline score will be considered the last non-missing observation before the first dose of pancreatic enzyme or placebo. The primary endpoint is the difference in mean CeD-GSRS score on treatment vs. placebo. Mean score for each participant will be generated by averaging the daily patient reported outcome (CeD-GSRS and CSI) scores across the study periods, such that there will be a single mean score per participant for the run-in phase and each treatment phase. The mean intrasubject score will then be averaged across the entire cohort for the relevant study phase.

We will use standard two-treatment cross over study analysis in which participant scores during drug treatment (GSRS_{rx}) for the primary outcome are compared to participant scores on placebo (GSRS_{pcb}). Assuming the data are normally distributed, if pancreatic enzyme supplementation is effective we would expect GSRS_{rx} < GSRS_{pcb}. The study as describe above is powered so that we will reach statistical significance if GSRS_{pcb} - GSRS_{rx} >0.4 using Student's paired t-test p<0.05.

Sensitivity analyses will be conducted using Mixed Model for Repeated Measures (MMRM). MMRM analyses will include treatment and study week as main effects, gender, baseline CeD-GSRS score as covariates, and weekly CeD-GSRS scores as repeated measures. Should data be non-normal, we will transform results into categorical data by calculating the proportion of patients with a >30% reduction in CeD-GSRS score on treatment and on placebo compared to their individual scores at baseline. If treatment is effective, we would expect a significantly greater proportion of patients to have a minimally clinically significant difference in GSRS score on treatment compared to placebo which can be evaluated using the Fishers Exact Test.

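### The primary paired t-test uses neither the period structure nor the CeD-GSRS scores collected just before each treatment period (days 7 and 24), so some precision may be left unused

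*Combined protocol and SAP*

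**What the plan says.** - **Primary analysis** (B3.B, Data Analysis): "We will use standard two-treatment cross over study analysis in which participant scores during drug treatment" are compared with scores on placebo by Student's paired t-test at the 5% level. No period, sequence or baseline term is named.
- **Sensitivity analysis** (same section): an MMRM with treatment and study week as main effects, and "gender, baseline CeD-GSRS score as covariates". Baseline is defined once per participant, as the last available value before first dosing. Phase means are listed for the run-in and the two treatment phases; the wash-out is not mentioned.
- **Collection** (B3.A, Number and Timing of Visits/Evaluations): the CeD-GSRS is completed "at the end of each study phase, i.e at days 7, 17, 24, and 34". Day 7 closes the run-in and day 24 closes the wash-out, so each treatment period has its own score just before it.
- **Sample size** (B3.B, Sample Size Justification): "a standard deviation of σ =0·55 is estimated"; "Allowing for a type-1 error rate of α =0·05"; "assuming a 10% drop-out rate"; "32 total participants would provide 80% power to detect a 0·4-point difference in CeD-GSRS score". The trial will "recruit until 30 participants have completed the treatment phases, up to a maximum of 40 eligible individuals".

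**The concern.** A participant may enter the second treatment period in a better or worse state than the first. The paired t-test leaves that difference in its error term, although days 7 and 24 measure it. A general shift between periods also stays in the error, because drug-first and placebo-first participants are pooled without a sequence term.

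The adjustment that is planned does not help here. A baseline shared by both periods drops out of the within-patient difference when both periods are observed. The difference between the two pre-period scores can explain variance in that contrast.

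What is at stake is precision, not validity. On the reading of the SD that best reproduces the stated sample size, 30 completers give slightly under the 80% target, so a few points of power would be useful.

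**Working it through.** **Inputs.** From B3.B: difference 0.4, SD 0.55, alpha 0.05, 30 completers. Assumed: a two-sided test, since the plan does not say. Not in the documents: rho, so a range is shown.

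**Reproducing the plan's figure.** The plan does not say what the SD of 0.55 refers to.
- As the SD of one period's score about the participant's own level, SD of the difference = 0.55 × √2 = 0.778. The normal approximation gives n = (1.96 + 0.84)² × 0.605 / 0.16 ≈ 30. The noncentral t gives n = 32 (power 80.5%) before drop-out. This matches 32 closely, although a t-based n with 10% drop-out would be 36.
- As the SD of the difference itself, n = 15 (normal) or 17 (t), or 17 to 19 with drop-out. This does not give 32.

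**Planned test at 30 completers.** Noncentrality = 0.4 / (0.778/√30) = 2.82 on 29 df: power 77.7%. With SD of the difference 0.55: 97.1%.

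**Adjusted model.** For each participant let d = score in phase 2 minus score in phase 4, s = +1 for drug first and −1 for placebo first, and b = day 7 minus day 24 score. Fit d = α + τs + βb + error. Here α absorbs any period effect and τ is the treatment effect. Residual SD = SD of the difference × √(1 − rho²), on 30 − 3 = 27 df.

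| rho | Power, SD of difference 0.778 | Power, SD of difference 0.55 |
|---|---|---|
| planned test | 77.7% | 97.1% |
| 0 | 77.5% | 97.0% |
| 0.2 | 79.1% | 97.5% |
| 0.3 | 81.2% | 98.0% |
| 0.4 | 84.2% | 98.7% |

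**How large might rho be?** Take phase-end scores with equal variances, and let r(k) be the correlation between scores k days apart. Then rho = [2r(10) − r(7) − r(27)] / [2(1 − r(17))].
- All scores equally correlated: rho = 0.
- Exponential decay with r(10) = 0.5: r(7) = 0.616, r(17) = 0.308, r(27) = 0.154, so rho = 0.230/1.384 = 0.17 and power is 78.6%.
- Very slow decay: the limit is (7 + 27 − 20)/(2 × 17) = 14/34 = 0.41, with power about 84.5%.
- Decay plus 30% measurement noise: rho is at most about 0.13, with power about 78%.

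Decay gives little because day 24 lies closer to the phase 2 score (7 days) than to the phase 4 score (10 days). Larger values need same-period correlation clearly above cross-period correlation: 0.7 against 0.5 gives (0.7 − 0.5)/(1 − 0.5) = 0.4.

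**Cancellation check.** In a simulated complete 30-patient crossover, the treatment estimate (−0.42583) and its standard error (0.1195) were identical with and without a common baseline covariate.

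**The sequence term alone.** Suppose, purely as an illustration, a 0.3-point shift between periods with balanced sequences. The variance seen by the paired t-test becomes about 0.605 + 0.09 × 30/29 = 0.698 (SD 0.836), and power falls to about 72%; direct simulation of the same case gives 73%. With a sequence term (28 df) power stays at 77.6%.

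**The case against.** **The planned test is valid.** The paired t-test addresses the stated endpoint, and this is a pilot. That stands: a reader might infer that the primary analysis is wrong, and nothing in the documents supports that.

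**The gain may be close to nil.** A reader might infer that appreciable power is certainly being discarded, for example about 10 points at rho 0.5 (88.0%). The documents give no rho, and 0.5 exceeds the simple-decay ceiling of 0.41. Further, if 0.55 is the spread of a period score across patients, an SD of the difference of 0.778 implies uncorrelated period scores, and decay then puts rho near 0. This limits the size of the point but leaves the sequence term and the conditional gain.

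**The fix adds an assumption.** Day 24 comes after randomised treatment. The unadjusted comparison needs no carry-over into the phase 4 score; the adjusted model also needs none at day 24. If a fraction L of the effect remains there, the estimate is multiplied by about 1 + βL/2. At β = 0.4 and L = 0.5 this is 1 + 0.4 × 0.5/2 = 1.10, about 10% inflation. With no drug effect there is nothing to carry over, so the test stays valid under the null. This stands as a real but modest cost.

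**The MMRM may do better than it appears.** Cancellation is exact only for complete pairs, and the modified intent-to-treat set admits participants with a single post-baseline assessment. If the weekly scores entered as repeated measures include day 24, that analysis uses it indirectly; the text does not settle this. A reader should not infer that the MMRM baseline is useless in every case.

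**Conclusion.** The point holds as an optional refinement of low severity. The two pre-period scores are collected, the primary test uses neither them nor the period structure, and a single baseline cannot sharpen the contrast in complete pairs.

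The covariate's effect on power at 30 completers runs from a loss of 0.2 points (rho 0) to a gain of about 7 points at the simple-decay limit, and is probably near the low end once measurement noise is allowed for. This assumes a two-sided test and an SD of the difference of 0.778. If that SD is 0.55, power is already 97% and little can be gained. The sequence term is worth having irrespective of rho, at almost no cost, but its benefit depends on a period shift that the documents do not quantify.

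**What to change.** In B3.B, Data Analysis:
1. Prespecify as primary a regression of each participant's period difference in the on-treatment CeD-GSRS score, as the plan defines that endpoint, on sequence and on the day 7 minus day 24 difference. Take the treatment effect from the sequence contrast.
2. Enter the baseline difference as a covariate, not as a change score. With equal variances, change scores multiply the variance by 2 − 2rho, which gives 63.4% power at rho 0.3.
3. Keep the unadjusted paired t-test as a sensitivity analysis, and use period-specific baselines in the MMRM.
4. Reconcile the descriptions of CeD-GSRS collection, so that outcome and period baselines are defined: daily in Data Analysis, phase-end in Number and Timing of Visits/Evaluations, weekly in Protocol Appendix A. State also whether the existing single baseline is the Visit 1 or the day 7 value, since the run-in is itself placebo.

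The cost is wording only, as the scores are already collected. Two degrees of freedom are spent (29 to 27, about 0.2 points of power), and the no-residual-effect assumption at day 24 should be stated. The choice should be fixed before unblinding, so that adjusted and unadjusted results cannot be selected between afterwards.

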Despite awareness in the celiac community of the potential for pancreatic exocrine insufficiency as a complication of celiac disease, there have been few prospective studies of pancreatic enzyme replacement in celiac disease and no studies to date that have taken place in the United States. As the population with celiac disease has expanded rapidly in recent years, 30 the potential for adjunctive therapies for celiac disease has become more apparent. In this study, we propose to conduct a rigorous prospective study of the utility of pancreatic enzyme replacement in celiac disease and assess the ability of fecal elastase levels to predict response to therapy.

Our goal is to provide adequate supplementation over the 10 day treatment period so as to maximize the opportunity for an evident therapeutic effect if indeed pancreatic enzyme insufficiency is contributing to the subjects' symptoms.

B3. DESCRIPTION OF RESEARCH PROTOCOL

A. Study Design – Overview, Methods, Procedures

Overview

This is a single-center investigator initiated phase IV trial to examine the efficacy of pancreatic enzyme supplementation in individuals with celiac disease who suffer persistent symptoms despite a gluten free diet.

Hypothesis

Pancreatic enzyme supplementation will improve symptoms in individuals with celiac disease who suffer persistent symptoms despite a gluten free diet.

Specific Aims:

Specific Aim 1: Evaluate the efficacy of pancreatic enzyme supplementation for reduction of gastrointestinal symptoms in patients with celiac disease on a gluten free diet.

Specific Aim 2: Assess the ability of fecal elastase levels to predict response to pancreatic enzyme supplementation in patients with celiac disease on a gluten free diet.

Primary Objective(s)/End Point(s):

The primary endpoint for Specific Aim 1 will be the average per individual subject on-treatment score in the Celiac Disease Gastrointestinal Symptom Rating Scale (CeD GSRS) domains of Diarrhea, Indigestion, and Abdominal pain comparing active treatment to placebo (i.e. a paired comparison of CeD GSRRS on treatment versus on placebo for each subject). The outcome measures used in the study and in particular the CeD GSRS have been employed previously by the investigators in their published studies. 31-33

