As a primary endpoint for Specific Aim 2, baseline fecal elastase measurement will be correlated to the average difference in on-treatment score in the CeD GSRS [active versus placebo].

Secondary Objective(s)/End Point(s):

- (1) Assessment of response to pancreatic enzyme supplementation in patients with celiac disease and either normal or low baseline fecal elastase levels.
- (2) Improvement in Celiac Symptom Index (CSI) with active treatment vs. placebo.
- (3) Reduction in number of total stools and loose stools (defined as a Bristol Score of 6-7) per week with active treatment vs. placebo.

Experimental Design & Number and Description of Each Treatment Arm/Group:

We propose a randomized, double blind, placebo-controlled, crossover trial of 40 participants overall. Participants would have a 7 day placebo run in period for documentation of symptoms at baseline (study phase 1), followed by a 10 day treatment/placebo period (study phase 2), after which there would be another 7 day wash out period (study phase 3) and a final 10 day cross over (study phase 4) resulting in a total study duration of 34 days.

Participants will be recruited from the Celiac Center at Beth Israel Deaconess Medical Center which currently has over 1900 registered patients with biopsy proven celiac disease. Patients will be enrolled in the out-patient clinic and though targeted mailings and advertisements. Males and Females over the age of 18 with biopsy-proven celiac disease and persisting symptoms despite adherence to a strict gluten free diet will be targeted 19.

Study visits would occur at screening (Visit 1), beginning of the third study phase (day 17-21, Visit 2) and study conclusion (day 35-40, Visit 3). Participants will regularly complete symptom surveys (Celiac Dietary Adherence Test [CDAT], to be administered at baseline; the CSI, to be administered daily; CeD-GSRS & a modified CSI, which are to be administered at the end of each study phase), a daily stool log (frequency and consistency), and a daily medication log. Participants will be contacted every 3 (±1) days after enrollment for safety and compliance assessments (e.g. medication, symptoms surveys, and stool log review).

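### The paired t-test named for the primary crossover comparison has no period term and drops MITT participants with one treatment phase; a treatment-plus-period mixed model handles both at little cost

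*Combined protocol and SAP*

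**What the plan says.** The protocol describes "a randomized, double blind, placebo-controlled, crossover trial of 40 participants overall" (B3.A, Experimental Design). It does not state how sequence is allocated. Phases 2 and 4 are the treatment phases; before them comes a "7 day placebo run in period for documentation of symptoms at baseline".

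The primary endpoint for Aim 1 is "a paired comparison of CeD GSRRS on treatment versus on placebo for each subject" (B3.A, Primary Objective(s)/End Point(s)). The Data Analysis section (B3.B) opens the primary comparison with "We will use standard two-treatment cross over study analysis", which could be read to include a period effect. The only test it then names for normally distributed data is the difference tested "using Student's paired t-test p<0.05". The outcome is a phase-level score: "there will be a single mean score per participant for the run-in phase and each treatment phase".

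The efficacy population requires at least one dose and at least one "post-baseline assessment (Modified Intent-to-Treat [MITT] population"). It does not require both treatment phases, and no imputation rule is given. A mixed model is planned: "MMRM analyses will include treatment and study week as main effects", with gender and baseline as covariates. It is labelled a sensitivity analysis.

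The Sample Size Justification assumes an SD of 0.55, a difference of 0.4, alpha 0.05 and 10% drop-out. It gives 32 participants for 80% power, and recruitment then runs until 30 have completed, with a maximum of 40.

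**The concern.** In a two-period crossover, each placebo-minus-active difference contains the treatment effect plus or minus any drift, with the sign set by sequence. The paired t-test handles this in two ways, depending on the split of completers between sequences.

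- **Equal split.** Drift cancels from the mean but stays in the estimated variance. The test is unbiased, conservative and less powerful.
- **Unequal split.** Part of the drift also moves the estimate, by drift × (n1 − n2)/n. With no stated allocation method and recruitment that stops on a count of completers, an equal split is not assured.

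Some drift is plausible. Participants qualify on a symptom threshold at Visit 1, receive dietary education, and start omeprazole on Day 1 if not already on a PPI. The run-in should absorb part of any early change, so only what remains between phases 2 and 4 matters.

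Separately, a participant with one treatment phase belongs to the MITT population but has no paired difference. The declared population and the named test therefore do not match, whatever the drift. Aim 1 rests on this one test.

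**Working it through.** **Inputs.** From the Sample Size Justification: SD 0.55, difference 0.4, alpha 0.05 (taken as two-sided), 32 participants, 10% drop-out, 30 completers. Assumed, because the documents do not give them: the drift, the split by sequence, and whether 0.55 is the within-participant SD or the SD of the paired difference.

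**The plan's own figure.** If 0.55 is the within-participant SD, the SD of differences is 0.55 × √2 = 0.778. Exact paired-t power is then 76.2% at n = 29, 77.7% at n = 30 and 80.5% at n = 32, so 32 is the number of completers needed. Allowing for drop-out, 32/0.9 rounds up to 36 enrolled; conversely, 32 enrolled less 10% is about 29 completers, with 76% power. An SD of differences of 0.742 would give 80% at 29. If 0.55 is itself the SD of differences, 17 completers suffice (80.4%), which does not reproduce 32. The main case therefore uses 0.778, which matches only approximately; the other two values show the range.

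**Model.** Difference = 0.4 ± drift + N(0, SD²), with the sign set by sequence.

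- *Paired t (29 df):* the mean difference is 0.4 + drift × (n1 − n2)/30. The residual sum of squares divided by SD² is noncentral chi-square with noncentrality drift² × (30 − (n1 − n2)²/30)/SD². Power is by numerical integration.
- *With period term (28 df):* the estimate is the average of the two sequence means, with standard error (SD/2) × √(1/n1 + 1/n2). Power is from the noncentral t and does not depend on drift.
- *Simple randomisation:* both are averaged over n1 ~ Bin(30, 0.5).

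**Power (%), simple randomisation, 30 completers**

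| SD of differences | Drift 0 | 0.1 | 0.15 | 0.2 | 0.3 | 0.4 | With period term | Break-even drift |
|---|---|---|---|---|---|---|---|---|
| 0.778 | 77.7 | 77.0 | 76.2 | 75.1 | 71.9 | 67.7 | 76.1 | 0.153 |
| 0.742 | 81.4 | 80.7 | 79.9 | 78.7 | 75.3 | 70.9 | 79.9 | 0.147 |
| 0.55 | 97.1 | 96.6 | 96.0 | 95.1 | 92.3 | 87.6 | 96.5 | 0.114 |

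Averaged over simple randomisation, the type I error of the paired t-test stays at 5%.

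**Given a particular split (SD 0.778)**

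- *15:15.* At drift 0.2 and 0.4, paired-t power is about 75.7% and 69.4%, with type I error 4.3% and 2.8%. With the period term, power is 77.6%.
- *18:12.* The estimate shifts by 0.2 × 6/30 = 0.04 or 0.4 × 6/30 = 0.08. The standard error is 0.778/√30 = 0.142, so the larger shift is 0.08/0.142 = 0.56 of a standard error. Depending on direction, paired-t power is 83% or 67% at drift 0.2, and 85% or 49% at drift 0.4. With the period term it is 76%.
- *20:10.* At drift 0.4 the type I error given that split is 10.3%.

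Under simple randomisation, a split at least as uneven as 18:12 has probability 2 × P(Bin(30, 0.5) ≥ 18) = 0.36, and one at least as uneven as 20:10 about 0.10. The mean absolute imbalance is 14% of n.

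**One-phase participants.** Take 15:15 complete pairs, add 2 or 4 participants with phase 2 only, and compute the generalised least squares variance of the treatment effect. With an assumed within-participant correlation of 0.3, the variance falls by 2.3% or 4.5%; with 0.7, by 1.0% or 2.0%. Power rises from 77.6% to 78.5% or 79.4%, and to 78.0% or 78.4%, a gain of 0.4 to 1.8 points. This needs missing-at-random.

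**The case against.** The paired t-test is not wrong. Averaged over simple randomisation it holds its 5% level, and at 18:12 its type I error is at most 5.3% even with a drift of 0.4. The documents give no drift, and below about 0.15 a period term loses power under simple randomisation. The larger gains need a residual drift of 0.3 to 0.4, close to or equal to the effect the plan calls clinically significant, and after a run-in. The planned MMRM already has study week and can use one-phase participants. The gain from those participants is small and needs missing-at-random, which may be doubtful where listed adverse effects of the drug (diarrhoea, indigestion) are also endpoint domains.

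All of this stands as a limit on the size of the point. It does not remove it. The MMRM is not the analysis on which Aim 1 is decided. If the announced crossover analysis was meant to include period, saying so costs nothing. The mismatch between MITT and the paired test exists at any drift.

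Two further remarks are fair. The Fisher's exact fallback for non-normal data also lacks a period term, and this change does not touch it. The plan averages daily CeD-GSRS scores but schedules the scale at the end of each phase (days 7, 17, 24 and 34). That needs settling, but it affects the t-test and the mixed model equally.

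**Conclusion.** The point holds, as a recommended improvement to a valid test and not as an error. The named primary test has no period term and cannot use every participant in the declared population.

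In the main case (30 completers, SD of differences 0.778, simple randomisation), a period term changes power by −1.6 points at no drift, +1.0 at drift 0.2 (76.1 − 75.1) and +8.4 at drift 0.4 (76.1 − 67.7). Beyond average power, it protects the realised estimate when drift and an uneven split occur together. Using one-phase participants adds perhaps 0.4 to 1.8 points. The size rests on the assumed drift, split, correlation and reading of 0.55; the mismatch between test and population rests on the text alone. Confidence is medium.

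**What to change.** In the Data Analysis section:

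- Make the primary analysis a linear mixed model of the single mean CeD-GSRS score per participant in phases 2 and 4, with treatment and period as fixed effects and participant as random effect, fitted to all MITT participants.
- State that the use of one-phase participants is valid under missing-at-random.
- State the sequence allocation method.
- Report the treatment difference with its 95% CI and the number of completers per sequence.
- Keep the paired t-test as a supportive analysis in participants with both phases, and the planned MMRM as the sensitivity analysis.

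The cost is SAP wording; no extra data are needed. With no drift and SD 0.778, the period term lowers power from 77.7% to 77.6% at 15:15, 77.4% at 16:14 and 75.9% at 18:12, and to 76.1% averaged over simple randomisation. Balanced sequence allocation would keep the loss near the low end.

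### If the data look non-normal, by no stated criterion, the paired CeD-GSRS comparison gives way to a >30% responder proportion tested by Fisher's exact test; a signed-rank test on the same differences keeps the question and more of the power

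*Combined protocol and SAP*

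**What the plan says.** All references are to section B3 of the combined protocol and SAP.

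- **B, Sample Size Justification.** "a standard deviation of σ =0·55 is estimated", and "a >0.4 point change in CeD-GSRS can be considered clinically significant". The conclusion is that "32 total participants would provide 80% power to detect a 0·4-point difference in CeD-GSRS score", "using a two treatment cross over design". A 10% drop-out rate is assumed, and recruitment runs until 30 patients complete, with at most 40 enrolled.
- **B, Data Analysis, primary comparison.** The within-patient contrast GSRS_pcb - GSRS_rx is judged "using Student's paired t-test p<0.05", on the premise of normal data.
- **B, Data Analysis, next paragraph.** After an MMRM sensitivity analysis comes the fallback: "Should data be non-normal, we will transform results into categorical data". Each patient is scored, on drug and on placebo, as having a reduction of more than 30% from his or her own baseline or not. The two proportions are compared by Fisher's exact test. The plan describes this cut as a minimal clinically significant difference.
- **B, Data Analysis, secondary outcomes.** These are to be handled in the same way as the primary endpoint: a t-test if normal, Fisher's exact test if not. This supports reading the fallback as reaching the primary analysis, although it is written in the sensitivity paragraph.

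The section names no normality test, no threshold, no variable to be checked and no blinded decision point. It names no rank-based, permutation or paired binary test.

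**The concern.** There are four linked problems.

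1. **The trigger is undefined.** The paired t-test needs only the within-patient differences to be roughly normal. Raw scores can look skewed while the differences behave well, for example because entry requires a highest-domain score of at least 3 (C, Subject Selection). The plan does not say which of the two would be checked, or how.
2. **The question changes.** The primary contrast needs no baseline. The fallback asks about percent change from baseline.
3. **Information is lost twice.** A continuous score becomes yes/no, and Fisher's exact test then treats two proportions from the same patients as independent groups.
4. **The cut does not match the plan's own threshold** of 0.4 points.

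At stake is a trial sized for a 0.4-point difference that reports, as its main result, a test for which no power was calculated and which may well miss that difference. With about 30 patients on a bounded symptom score, a finding of non-normality is quite possible.

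**Working it through.** **Inputs from the plan.** Difference 0.4; SD 0.55; alpha 0.05; stated N 32 at 80% power; drop-out 10% (32 × 0.9 = 28.8, about 29 completers); target 30 completers. Sidedness is not stated; two-sided is assumed because it reproduces the stated N. The plan does not say whether 0.55 is the per-period SD or the SD of the differences.

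**Step 1: reproduce the plan's figure.** Read 0.55 as the per-period within-subject SD, so that SD of differences = 0.55 × √2 = 0.778. Power comes from the noncentral t with n - 1 degrees of freedom and noncentrality 0.4 / (0.778/√n).

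- n = 32: noncentrality 2.91, power 80.45%; 32 is the smallest n that reaches 80%.
- n = 30: noncentrality 2.82, power 77.7%.
- n = 29: noncentrality 2.77, power 76.2%.

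The stated 32 is therefore reproduced. Reading 0.55 as the SD of differences gives n = 17 instead, and 97% power at n = 30. One-sided testing gives 25 or 14, depending on the SD reading.

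**Step 2: the cut-off against the 0.4-point threshold.** A 30% reduction equals 0.4 points when baseline = 0.4/0.30 = 1.33. At an assumed baseline of 3 it is 0.30 × 3 = 0.9 points, and 0.9/0.4 = 2.25 times the threshold.

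**Step 3: power of the fallback.** The documents give no baseline mean, baseline SD or responder rate, so these are assumptions: mean baseline 2.5 to 4, placebo improvement 0 to 1.0 points, between-patient SD 0.6, score floor 1. With true difference 0.4, per-period SD 0.55, n = 30 and 2,500 simulated trials per scenario:

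- Normal errors: Fisher 4-30%, exact McNemar on the same dichotomy 5-38%, paired t 65-78% (the low end reflects the assumed floor).
- Skewed (lognormal) errors, the case in which the fallback would fire: Fisher 0.1-71%, paired t 58-81%, signed-rank 74-94%.

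A second set of scenarios at the same effect, n and SD gave Fisher 5-31% against signed-rank 70-78% (normal), and Fisher 0-83% against signed-rank 89-99% (skewed). Together, Fisher spans about 4-31% (normal) and 0-83% (skewed). The signed-rank test was ahead of Fisher in every scenario.

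Some skewed scenarios show how far the result depends on the assumptions:

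| Baseline | Placebo improvement | Responders, drug / placebo | Fisher | McNemar | Paired t | Signed-rank |
|---|---|---|---|---|---|---|
| 4.0 | 0 | 7% / 3% | 0.1% | 0.1% | 80.9% | 92.8% |
| 3.5 | 0.3 | 25% / 8% | 22.1% | 36.6% | 81.0% | 93.2% |
| 3.0 | 1.0 | 83% / 62% | 33.0% | 38.4% | 72.8% | 88.2% |
| 3.5 | 0.6 | 50% / 18% | 71.0% | 83.6% | 80.7% | 92.5% |

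**Step 4: the other SD reading.** If 0.55 is the SD of differences (per-period 0.55/√2 = 0.389), normal errors give paired t 92-97% and Fisher 0.4-58%. The skewed scenarios at n = 30 give Fisher 0-92% and signed-rank 94-100%, with signed-rank again ahead in each.

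**Step 5: error rate of the two-stage rule.** The plan names no normality test, so assume Shapiro-Wilk at 0.05 on the differences, then paired t or Fisher. Under no effect (1,200 trials per scenario), rejection was 3.8-4.8% with normal errors and 1.3-2.1% with lognormal errors. A second check with 300 trials per scenario gave 0.3-6.0%. Its simulation standard error at 5% is √(0.05 × 0.95/300) = 1.3 percentage points, so 6.0% is compatible with 5%.

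**The case against.** The strongest defence has four parts.

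- **The fallback is pre-specified.** A reader might infer that the test is picked once the results are known. The text does not support that: the 30% cut, the comparison with own baseline and Fisher's test are all fixed in advance. Only the switch depends on the data.
- **The 5% error rate is not shown to suffer.** A reader might infer inflation from a data-dependent switch. Step 5 found none of any size, and Fisher on positively correlated pairs was conservative. What remains is room for discretion in calling the data non-normal.
- **The power of the plan is not the power of the fallback.** Under the Shapiro-Wilk version of the rule with a true 0.4 difference, the fallback fired in only 4-17% of trials with normal errors, and overall power was 61-75%. With skewed errors overall power was 38-77%, so a loss remains, but its size depends on the assumptions.
- **Context.** The plan calls the trial a pilot and its sample size not definitively calculable, and it also plans an MMRM. However, it states 80% power and a significance criterion, and MMRM is itself a normal-theory method, so neither fact answers the point in full.

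It is also tempting to say that dichotomising loses most of the power even with a correctly paired test. That is not general: in the last row of the table McNemar (83.6%) exceeds the paired t-test (80.7%).

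**Conclusion.** The point holds in this form: a pre-specified but inefficient fallback, behind an undefined data-dependent trigger, replaces the paired primary comparison with a different question at a cut that does not match the plan's 0.4-point threshold.

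No single figure for the loss can be drawn from the documents. A narrow band such as 12-26% for Fisher needs assumed baselines and normal errors, under which the fallback is not meant to apply. What can be said is that the stated 80% does not carry over to the fallback. At per-period SD 0.55, the range for Fisher is wide and often low, and the signed-rank test on the same differences did better throughout. That ordering, rather than any one power value, is the firm result. It rests on a constant 0.4-point shift and on the error shapes simulated. The missing criterion and the change of question rest on the text alone.

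This should be corrected before unblinding. It does not invalidate the design.

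**What to change.** In B3.B, Data Analysis:

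1. Keep the paired comparison of GSRS_pcb - GSRS_rx as the primary analysis whatever a normality check shows.
2. Pre-specify the Wilcoxon signed-rank test, or a sign-flip permutation test, on the same within-patient differences as the robustness analysis and the only fallback. If a switch is kept at all, state the variable (the differences), the criterion, and that the decision is made blinded.
3. Keep the >30% responder proportion as a supportive summary, tested with a paired method such as McNemar's, and either justify the cut against the 0.4-point threshold or stop calling it a minimal clinically significant difference.
4. Apply the same rule to the continuous secondary endpoints, which now carry the same t-test/Fisher split.
5. In Sample Size Justification, say which SD 0.55 is, and that the 80% refers to the paired t-test.

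The cost is SAP wording. The tests are standard, and no new data, visits or patients are needed.
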